# The following scales will be completed at the Week 12 (Visit 6)/Early Termination Visit: BPI-DPN, PGI-C, QOL-DN, PCS and S-STS.

A safety follow-up telephone call will be made to the subject within 7-10 days and then approximately 30 days after Visit 6 / Week 12 to assess for any AE/SAE closure and any newly reported SAEs.

#### Number of subjects:

Approximately 204 subjects will be randomized.

Inclusion Criteria: Screening

Subjects must meet ALL the following criteria to be enrolled in this study:

- 1. An Institutional Review Board approved written informed consent and privacy language (Health Insurance Portability and Accountability Act (HIPAA)) authorization must be obtained from the subject prior to performing any study-related procedures.
- 2. Consent to being included in a research subject database.
- 3. Subject is  $\geq 18$  and  $\leq 75$  years of age.
- 4. Diagnosis of Type 2 Diabetes.
- 5. At least moderate pain intensity over the last week as assessed by PGI-S at Visit 1.
- 6. Hemoglobin A1c (HbA1c)  $\leq 11\%$  (measured at Visit 1).
- 7. Stable use of diabetic medications beginning 1 month prior to Visit 1 (adequate glycemic control with diet and exercise alone is also permitted).
- 8. Diabetic peripheral neuropathy, of symmetrical nature and in lower extremities for ≥4 years (DPN in the upper extremities is not exclusionary).
- 9. Presence of pain due to diabetic neuropathy for at least 6 months prior to screening.
- 10. Total score of  $\geq 4$  on the Michigan Neuropathy Screening Instrument.
- 11. Body mass index  $\leq$ 40 kg/m^2.
- 12. Absence of impaired hepatic function. Impaired hepatic function is characterized by a previous known diagnosis of chronic liver disease, and/or abnormal serum total bilirubin (TBL), or alanine transaminase (ALT), aspartate transaminase (AST), or alkaline phosphatase (ALP) >1.5x upper limit of normal (ULN) at screening.
- 13. Calculated creatinine clearance  $\geq 60$  mL/minute (Cockcroft-Gault formula).
- 14. Fasting triglycerides 600 mg/dL.
- 15. Except as noted in criteria 12-14 above, clinical laboratory values must be within normal limits, or deemed not clinically significant by the investigator.
- 16. Female subjects of child bearing potential with a negative pregnancy test prior to entry into the study and who are practicing a highly effective method of birth control (e.g., oral or parenteral contraceptives, intrauterine device, barrier [condom and spermicide], abstinence) and who do not plan to become pregnant, breastfeed or donate ova during the course of the study and for 28 days after the final administration of investigational product.
- 17. Male subjects should use a highly effective method of birth control and refrain from sexual activity with female sexual partners who do not use a highly effective method of birth control during the study. Male subjects who are not surgically sterilized for at least 90 days prior to screening, and sexually active with female partner(s), must agree to use barrier contraception (condom with spermicide) during the study. Subjects must agree to refrain from sperm donation during the study and for 90 days after the final administration of investigational product.
- 18. Has not participated in an interventional study for at least 30 days or has not taken study medication for a period of at least 5 half-lives of the study medication, whichever is longer. Agrees not to participate in another interventional study while on treatment. Eligibility will be reviewed during the study via sponsor participation in a research subject database.
- 19. Ability to understand the requirements of the study, abide by the study restrictions, as well as concomitant medications exclusions, and agree to return for the required assessments.
- 20. Subject agrees not to initiate or change any non-pharmacologic interventions (including normal daily exercise routines, chiropractic care, physical therapy, psychotherapy, and massage therapy) during the study. Any ongoing non-pharmacologic intervention must be stable for at least 30 days prior to screening.

Inclusion Criteria: Randomization

Daily pain scores and diary compliance will be transferred into the interactive response technology system, which will be used to assess the criteria for randomization. Subjects whose mean of the daily average pain intensity score during the preceding seven (7) days is within the protocol-defined algorithm and with adequate compliance with daily diary completion will be eligible for randomization.

Waivers to the inclusion criteria will NOT be allowed.

#### Exclusion Criteria:

Subjects who meet ANY of the following criteria will be excluded from the study:

- 1. Current diagnosis of a major psychiatric disorder (including schizophrenia and/or bipolar disorder), including those who have required an antipsychotic (e.g., aripiprazole, asenapine, cariprazine, clozapine, lurasidone, olanzapine, quetiapine, risperidone, ziprasidone) or mood stabilizer (e.g., lithium, carbamazepine, lamotrigine, valproate) for a psychiatric condition in the past year, or subjects who have had a major depressive episode (MDE) in the past 6 months. Subjects with major depressive disorder (MDD), generalized anxiety disorder (GAD) or panic disorder who have been on stable medication for the past 3 months (and are expected to remain stable for the duration of the study) and whose condition is currently well-controlled may be included.
- 2. Pain that cannot be clearly differentiated from, or could interfere with, the assessment of peripheral diabetic neuropathy, as measured by the Masquerading Disorders Tool at Visit 1.
- 3. Neurologic disorders unrelated to diabetic neuropathy (e.g., phantom limb from amputation), skin condition in the area of neuropathy that could alter sensation (e.g., plantar ulcer), or other painful conditions (e.g., arthritis) that, in the judgment of the investigator, could interfere with reporting of pain due to diabetic neuropathy.
- 4. History of hypoglycemia that disturbed consciousness, or ketoacidosis requiring hospitalization within the past 3 months.
- 5. History of severe renal impairment defined by renal dialysis or peritoneal dialysis or has undergone renal transplant.
- 6. Known history of significant cardiovascular condition, such as myocardial infarction within the past year, or moderate to severe congestive heart failure (New York Heart Association (NYHA) Class III and IV), or evidence of current uncontrolled cardiac arrhythmias, angina, or electrocardiographic evidence of acute ischemia or clinically significant conduction system anomalies; QTcF >450 msec (males) or >470 msec (females), or uncontrolled hypertension characterized by resting systolic blood pressure >160 mm Hg or resting diastolic >100 mm Hg, or clinically significant hypotension in the judgement of the Investigator as characterized by resting systolic blood pressure <60 mm Hg accompanied by symptoms such as lightheadedness, dizziness, and profound fatigue or signs such as irregular heartbeat.

- 7. Pulse rate <45 bpm or >90 bpm.
- 8. History of Huntington's disease, Parkinson's disease, Alzheimer's disease, multiple sclerosis, or a history of seizures (with the exception of childhood febrile seizures), epilepsy, or stroke.
- 9. Positive serology test result for HIV or current hepatitis B or C infection, or other ongoing infectious disease that the investigator considers clinically significant.
- 10. Concomitant use of protocol specified prohibited medications and is unable to wash out (see Section 8.7 of the protocol for Concomitant Medications Restrictions).

a. Washout from excluded medication allowed only if the Investigator deems it medically appropriate.

b. Washout should be completed during screening, with the last dose being at least two (2) weeks prior to randomization (See Section 15.1 of the protocol for Disallowed Analgesic and Other Medications).

11. Current or recent (within 12 months of screening) history of a substance use disorder including cannabinoid use disorder.

#### 12.

- a. Visit 1: Positive urine drug screen for benzodiazepines or opioids inconsistent with current prescriptions, psychoactive cannabinoids (e.g., marijuana, THC) inconsistent with subject reported use, PCP, cocaine, or amphetamines at Visit 1.
- b. Visit 2: Positive urine drug screen for benzodiazepines inconsistent with protocol specified allowed prescriptions, psychoactive cannabinoids (e.g., marijuana, THC) inconsistent with subject reported use, opioids, PCP, cocaine, or amphetamines, at Visit 2.
- Sensitivity or allergy to, or concomitant use of N-methyl-D-aspartate receptor ligands including ketamine, esketamine, amantadine, dextromethorphan, memantine, methadone, dextropropoxyphene, lamotrigine, and/or ketobemidone.
- 14. Use of NMDAR-binding drugs (e.g., ketamine, esketamine, amantadine, dextromethorphan, memantine, methadone, dextropropoxyphene, lamotrigine, and/or ketobemidone) within 30 days prior to dosing or during the study. Use of high concentration capsaicin patch within 3 months prior to screening; use of lidocaine patch within 1 month prior to screening.
- 15. Sensitivity to or intolerance to acetaminophen or associated formulation components.
- 16. Hypersensitivity or intolerance to multiple medications, in the opinion of the investigator.
- 17. Amputations of lower extremities (toe(s) amputation is allowed).
- 18. Meets the criteria for suicidal intent, plan and/or behavior by scoring 3 or 4 on Questions 2 or 13, or 2 or higher on any Question 1a (only if 1b is coded YES), 3, 4, 5, 6, 7, 8, 9, 10, 11, 12 or 14 based on the S-STS or who is at significant risk to commit suicide, as assessed by the investigator, at Visit 1 or Visit 2.
- 19. Planned surgery during study participation.
- 20. Active malignancy or a history of malignancy (except for treated non-melanoma in-situ skin cancer) within 5 years of screening.
- 21. Employee, contractor, or volunteer of the study site, CRO, or Aptinyx, or relative of any employee, contractor, or volunteer of the study site, CRO, or Aptinyx.
- 22. Any condition, including serious medical conditions that could interfere with the ability of the subject to participate in the study or could confound study assessments. Presence of an exclusionary masquerading disorder in the Masquerading Disorders Tool (MDT) assessment.
- 23. Subject has evidence of any clinically significant, uncontrolled gastrointestinal, endocrinologic, hematologic, immunologic, metabolic, urologic, pulmonary (including uncontrolled, obstructive sleep apnea), neurologic, dermatologic, and/or other major disease (exclusive of diabetes) that may interfere with study participation, as assessed the investigator.
- 24. Previous randomization in current or previous NYX-2925 clinical trials.
- 25. Subject has filed for a disability claim or has any pending worker's compensation litigation.
- 26. History of severe infection with COVID-19 requiring hospitalization, treatment with oxygen or mechanical ventilation, that may interfere with study participation, as assessed the investigator.
- 27. Any subject with a medical history of COVID-19 infection (positive test) within the last two (2) months, or current symptoms consistent with COVID-19 infection (not tested), e.g. loss of smell, sore throat, cough or fever (2 or more symptoms at the same time), as assessed by the investigator.

Waivers to the exclusion criteria will NOT be allowed.

#### Test product, dose and mode of administration, batch number:

NYX-2925 50 mg oral capsules, single capsule once daily by mouth.

#### Reference therapy, dose and mode of administration, batch number:

Placebo, oral capsules, single capsule once daily by mouth

#### **Rescue medication:**

Acetaminophen, up to 2 g/day, as needed for DPN related pain. To be dispensed in beginning at Visit 1 and re- dispensed and/or replenished throughout the entire study.

#### Duration of study:

**Screening:** One (1) to four (4) weeks. Prohibited analgesic medications for diabetic peripheral neuropathy need to be discontinued with the last dose taken at least two (2) weeks prior to randomization. **Maintenance**: Twelve (12) weeks of blinded treatment with either NYX-2925 50 mg QD or placebo QD.

#### Criteria for evaluation:

#### Efficacy endpoint:

Primary efficacy endpoint:

• Change from baseline in the weekly mean of the daily Numeric Rating Scale (NRS) score assessing average pain intensity related to DPN in the past 24 hours.

Secondary efficacy endpoints:

- Change from baseline in the weekly mean of the Daily Sleep Interference Scale (DSIS) scores at Week 12.
- Percentage of subjects 'much improved' or 'very much improved' on Patient Global Impression of Change (PGI-C) at Week 12.
- Percentage of subjects achieving ≥30% pain reduction from baseline in the weekly mean NRS average pain intensity related to DPN at Week 12.
- Percentage of subjects achieving ≥50% reduction from baseline in the weekly mean NRS average pain intensity related to DPN at Week 12.
- Change from baseline to Week 12 in the Norfolk Quality of Life Questionnaire Diabetic Neuropathy (QOL-DN) score.
- Use of rescue medication, including the proportion of subjects using rescue medication, the frequency and amount used.
- Cumulative response (percent reduction from baseline) in the weekly mean NRS average pain intensity at Week 12.
- Change from baseline in the weekly mean of the daily Numerical Rating Scale (NRS) at each week from Week 1 through Week 12.

Other efficacy endpoints:

Sample Size:

The planned sample size is a total of 204 randomized subjects. This will provide approximately 80% power using statistical testing with an overall Type I error rate of 0.05.

#### Statistical methods:

Safety analyses will be based on the Safety Population, which is defined as all subjects who receive at least one (1) dose of study drug. Efficacy analyses will be based on the modified Intent-to-Treat Population, which is defined as all subjects in the Safety Population with at least one 1 post baseline assessment of the weekly mean of pain intensity NRS.

Change from baseline will be assessed for treatment group differences using a Mixed Model for Repeated Measures (MMRM) with factors for study site, treatment, week, treatment-by-week interaction, and including the baseline value of the response variable as a covariate.

An analysis of covariance (ANCOVA) model with fixed factors of study site and treatment, and using the baseline value as a covariate will be done as a sensitivity analysis.

Change in the weekly mean of the daily NRS score assessing average pain intensity in the past 24 hours from baseline will be assessed using analogous MMRM and ANCOVA models as described for the primary efficacy endpoint above. Change from baseline for weekly mean NRS score for average pain upon walking and worst daily pain, DSIS, BPI-DPN, PCS and QOL-DN will be analyzed similarly. The PGI-C will be summarized at each evaluation.

The use of rescue medication will be summarized descriptively. The percentage of subjects achieving  $\geq$ 30% reduction, percentage of subjects achieving  $\geq$ 50% reduction, and sustainability of  $\geq$ 30% and  $\geq$ 50% reduction in the weekly mean NRS average pain intensity related to DPN will be summarized.

The number of days to the first  $\geq$ 30% reduction and number of days to the first  $\geq$ 50% reduction in the weekly mean NRS average pain intensity related to DPN will be assessed for treatment group differences using the log-rank test or other applicable test.

Adverse events will be categorized by system organ class and preferred term with the Medical Dictionary for Regulatory Activities (MedDRA). Summary tables for treatment-emergent adverse events (TEAEs) will include number and percent of subjects experiencing TEAEs by system organ class and preferred term.

Mean change in clinical laboratory results and vital signs from baseline will be summarized descriptively. Clinical laboratory results considered clinically important by the investigator will be identified.

Subjects with suicidal ideation or behavior will be identified with the S-STS.

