### **12.4.** Analysis Populations

Safety analyses will be based on the Safety Population, defined as all subjects who receive at least one dose of study drug.

Efficacy analyses will be based on the modified Intent-to-Treat Population, defined as all subjects in the Safety Population with at least one postbaseline assessment of the pain intensity NRS.

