6.1.4 Modified Intent-to-Treat Population

The Modified Intent-to-Treat (mITT) Population includes all subjects in the Safety Population with at least one post-baseline assessment of the pain intensity NRS. Efficacy analyses for the mITT Population will have subjects grouped based on their planned treatment. All efficacy analyses will be performed on the mITT Population.

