6.2.17.3 Definition of ≥30% and ≥50% Responder

Subjects who achieve a percent reduction in NRS score relating to 'Average pain intensity related to DPN in the past 24 hours' of \geq 30% (programmatically, where the change from baseline value is \leq -30) at Week 12 will be classified as responders, and non-responders otherwise.

Similarly, subjects who achieve a percent reduction in NRS score relating to 'Average pain intensity related to DPN in the past 24 hours' of \geq 50% (programmatically, where the change from baseline value is \leq -50) at Week 12 will be classified as responders, and non-responders otherwise.

Subjects with missing weekly mean NRS score relating to 'Average pain intensity related to DPN in the past 24 hours' at Week 12 will be classified as non-responders.

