6.2.20 Patient Global Impression of Change

Patient Global Impression of Change (PGI-C) is a 7-point scale (1 to 7; where 1 corresponds to 'very much improved, 4 is 'no change', and 7 is 'very much worse') that captures the subjects' impression of their overall change since the beginning of the study to specific time points during the study.

For the analysis, subjects will be classified as either responders, that is, a PGIC response of 1 ('very much improved') or 2 ('much improved'), or non-responders, that is, all other PGIC responses (recorded as 3, 4, 5, 6 and 7) at Week 12. Subjects will be classified as non-responders if their PGIC assessments at Week 12 are missing.

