A similar approach in modeling the REML-based MMRM as in the primary analysis will be applied to the weekly dosage of acetaminophen used except that the outcome variable will be the dosage of acetaminophen used at Weeks 1 through 12, and the fixed effects are as follows: study site, treatment group, week, and treatment-by-week interaction as terms in the model. The LS means, corresponding SEs, and 95% CIs for each treatment group will also be presented at each

week. Additionally, estimate, corresponding SE, and p-value of the treatment difference at each week will also be presented.

[figure not shown]
6.11.2.6 Cumulative response (percent reduction from baseline) in the weekly mean NRS average pain intensity at Week 12

[figure not shown]
A cumulative responder analysis will be conducted for the primary efficacy endpoint. in this analysis, response is defined as any percent reduction from baseline in the weekly mean NRS average pain intensity at Week 12. Subjects who do not achieve a reduction from baseline at Week 12, who have a missing result, or who prematurely discontinue from treatment prior to Week 12 will be defined as a non-responder (i.e., 0% reduction/improvement in percent reduction from baseline). A cumulative response curve will be generated in which the response level is on the x-axis (0-100%, in 10% intervals, with reference lines at 30% and 50%) while the associated cumulative proportion of subjects calculated for that response level (i.e., percent reduction from baseline) is on the y-axis. The difference in the cumulative response curves between treatment groups will be analyzed using a Kolmogorov-Smirnov test. This test determines if two samples of data are from the same distribution. The D statistic and associated p-value will be provided.

[figure not shown]
```
PROC NPAR1WAY DATA= DATAIN;
CLASS TREATMENT;
VAR RESP;
EXACT KS;
RUN;
```

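### Dosed subjects with no post-dose pain diary drop out of the responder denominators before the missing-equals-non-response rule can reach them

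*Protocol*

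**What the plan says.** **Population.** SAP 6.1.4 defines the mITT set as one that "includes all subjects in the Safety Population with at least one post-baseline assessment of the pain intensity NRS", grouped by planned treatment, and adds: "All efficacy analyses will be performed on the mITT Population". SAP 6.11.2 repeats this for the secondary endpoints. Protocol 12.4 has the same definition: "all subjects in the Safety Population with at least one postbaseline assessment of the pain intensity NRS". The protocol synopsis differs in asking for a weekly mean: "all subjects in the Safety Population with at least one 1 post baseline assessment of the weekly mean of pain intensity NRS". Every efficacy table in SAP section 11 is labelled mITT; none is listed on all randomized or all dosed subjects.

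**Missing Week 12 results.** Three SAP rules score a missing result as failure:
- ≥30% and ≥50% response (6.2.17.3): subjects with a missing weekly mean NRS "at Week 12 will be classified as non-responders".
- PGI-C response (6.2.20): "Subjects will be classified as non-responders if their PGIC assessments at Week 12 are missing".
- Cumulative response (6.11.2.6): "Subjects who do not achieve a reduction from baseline at Week 12, who have a missing result, or who prematurely discontinue from treatment" before Week 12 are non-responders with 0% reduction.

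**The concern.** The first dose is taken in the clinic at Visit 2 (Protocol 6.1), so a subject joins the Safety Population at that moment. Whether the subject also joins the mITT set depends on something that happens afterwards: entering at least one later pain score. Someone who is dosed and then stops at once, entering nothing, has the most complete form of missing outcome. Such a subject is removed rather than scored as a failure.

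For the four responder-type analyses, the groups compared are then no longer the randomized and dosed groups. An arm that loses more subjects at the very start has its response rate raised relative to the other arm. PGI-C response also becomes conditional on a pain diary, which is a different instrument.

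**Working it through.** **1. Planned numbers.** SAP section 4 gives a difference of 0.73, SD 1.7, two-sided alpha 0.05, about 80% power and 15% drop-out; SAP section 5 gives 1:1 allocation.

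- n per arm = 2 × [1.7 × (1.960 + 0.842) / 0.73]² ≈ 85.1, rounded up to 86.
- 86 / 0.85 = 101.2, rounded up to 102 per arm, or 204 in total.

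This reproduces the stated 204, so sample size is not at issue. I use 102 dosed per arm below.

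**2. How the rules treat three early leavers.** The date of first dose is Day 1 (SAP 6.2.3), the NRS baseline ends at Day -1 (6.2.17.1), and a last diary on Day 1 to Day 10 is assigned to Week 1 (6.2.17.2). The 5-of-7 minimum is stated for the baseline mean only.

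| Subject | In mITT? | ≥30% / ≥50% / cumulative | PGI-C response |
|---|---|---|---|
| Dosed, one bedtime score that evening, then leaves with no Week 12 data | Yes | Non-responder | Non-responder |
| Dosed, no later score, leaves with no Week 12 data | No | Not counted | Not counted |
| Dosed, no later score, but has a Week 12 PGI-C | No | Not counted | Observed value discarded |

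The first two subjects differ by a single diary entry. For the NRS endpoints, an excluded subject would always be a non-responder under the SAP's rule, because no Week 12 weekly mean can exist. For PGI-C this is not certain. Under SAP 6.2.12 an early-withdrawal PGI-C maps to Week 12 only from Day 71, so the third case is rare, but it is possible.

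**3. Size on a binary endpoint.** The documents give neither the number excluded nor expected response rates, so both are assumed. Let r₁ and r₂ be the responders, and k₁ and k₂ the excluded non-responders, on active and placebo. The mITT proportions are r₁/(102 − k₁) and r₂/(102 − k₂). The pooled test is z = (p₁ − p₂) / √[p(1 − p)(1/n₁ + 1/n₂)].

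Assumed r₁ = 48, r₂ = 35:

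| Excluded (active, placebo) | Rates | Difference (points) | p |
|---|---|---|---|
| 0, 0 (all dosed) | 47.1% vs 34.3% | 12.7 | 0.064 |
| 1, 0 | 47.5% vs 34.3% | 13.2 | 0.056 |
| 2, 0 | 48.0% vs 34.3% | 13.7 | 0.048 |
| 4, 0 | 49.0% vs 34.3% | 14.7 | 0.035 |
| 2, 2 | 48.0% vs 35.0% | 13.0 | 0.062 |
| 4, 4 | 49.0% vs 35.7% | 13.3 | 0.060 |
| 0, 4 | 47.1% vs 35.7% | 11.3 | 0.104 |

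The SAP's test for these endpoints is an unstratified CMH test (6.11.2.2), which barely changes the result: 0.065 for 0, 0 and 0.036 for 4, 0.

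A second assumed case, 41 vs 28 responders, behaves the same way: p = 0.054 on all dosed, 0.042 with 2, 0 excluded, 0.051 with 5, 5, and 0.093 with 0, 5. Both cases were chosen near 0.05 to show sensitivity; they are not predictions. Cumulative response uses a Kolmogorov-Smirnov test, which I did not recompute.

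**4. Primary analysis and its stress test.** In the MMRM a subject with no post-baseline value contributes no outcome record, so the estimate is essentially unchanged. If k active subjects with no post-baseline data were added to the placebo-based imputation with zero expected effect, the planned difference would become 0.73 × (1 − k/102): 0.716 at k = 2 and 0.694 at k = 5.

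**The case against.** **The set is declared and consistent.** The requirement for a post-baseline NRS appears in Protocol 12.4, in SAP 6.1.4 and in the estimand's population attribute (Protocol 12.6.1.1, SAP 6.11.1.1). The missing-data rules can be read as operating inside that set. This stands. A reader might infer that the SAP contradicts itself; it does not. The population definition limits the reach of the missing rule, which is weaker.

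**Few subjects can be affected.** Diaries are completed nightly, only subjects with adequate diary compliance are randomized, and one entry on the evening of Day 1 suffices. This also stands: at zero or one subject per arm the effect is very small unless a result sits right at the threshold.

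**No reason to expect imbalance.** Protocol 6.3 reports no difference from placebo in the adverse event profile of the first Phase 2 study. A reader might infer that the exclusion favors NYX-2925; the documents do not support a direction, and the 0, 4 row shows the opposite shift.

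**Low stakes and visible exclusions.** Secondary endpoints carry no multiplicity adjustment (SAP section 9, item 10), so a nominal p-value crossing 0.05 supports no confirmatory claim. Exclusions are counted by arm (SAP 6.4) and listed with reasons (SAP 6.1). That lets a reader rebuild the denominators, but it does not replace a planned analysis.

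**The sensitivity analyses test something else.** A reader might infer that the pattern-mixture and tipping-point analyses are defective because they omit the earliest leavers. SAP 6.11.1.3 presents them as tests of the MAR assumption in the primary analysis. Running them on the same set as the MMRM isolates that assumption; moving them would change population and missing-data assumption together.

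**Conclusion.** The point holds as an inexpensive improvement to four secondary analyses. They are run on a set selected after randomization and dosing, and dosed subjects with no later pain score escape the SAP's non-response rule. Small equal losses move the response difference by well under one percentage point (12.7 to 13.3 at four per arm in the worked case). Losses of two to four in one arm only move it by about 1 to 2 points, in either direction, and can carry a borderline p-value across 0.05. These sizes rest on assumed responder and exclusion counts and on excluded subjects being non-responders, which is exact for the NRS endpoints and only likely for PGI-C. It would therefore go too far to call every excluded subject a certain failure. The synopsis wording is an editorial mismatch: with no minimum diary count stated for post-baseline weeks, a weekly mean and a single score select essentially the same subjects.

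**What to change.** In SAP 6.1.4 and 6.11.2:

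- Keep the mITT set for the MMRMs.
- Analyze ≥30% response, ≥50% response, PGI-C response and cumulative response in all randomized subjects who took at least one dose, by planned treatment.
- Count a missing Week 12 NRS as non-response (0% reduction). Use an observed Week 12 PGI-C as recorded, and count only a missing one as non-response.
- Keep the pattern-mixture and tipping-point analyses on mITT. If wanted, add one placebo-based imputation run on all dosed subjects as a separate, labelled analysis; baseline and site are already in the imputation model.
- Align the synopsis definition with Protocol 12.4 and SAP 6.1.4.

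The cost is SAP wording and one population flag, with no new data and no change to the sample size or primary model. Response rates will fall slightly wherever non-responders are added, and the responder and MMRM tables may show slightly different Ns, which a footnote can explain.
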